# **13.9** Safeguards for vulnerable populations and sensitive procedures Urine pregnancy testing will be performed on all persons of pregnancy potential at the time of admission for both Visit 1 and Visit 2. This pregnancy test will be considered valid for the entire period of the inpatient admission. Further, additional pregnancy testing will be performed 24 hours prior to MRI scans performed in the NIH NMR center and prior to the use of ionizing radiation, such as DEXA, and fluoroscopy-guided LP.

Protections for employees and staff participating in this study include 1) assuring that the participation or refusal to participate will have no effect, either beneficial or adverse, on the subject's employment or position at the NIH, 2) giving employees and staff who are interested in participating the "NIH Information Sheet on Employee Research Participation" prior to obtaining consent, and 3) assuring that there will be no direct solicitation of employees or staff. 4) Independent consent monitoring will be provided by the NIH HSPU or the Bioethics Department.

To ensure that research staff are adequately trained to respect the privacy and confidentiality of NIH employees and staff, study investigators and staff are required to complete the CITI "Just in Time" Training: Vulnerable Subjects – Workers/Employees.

This study collects sensitive information on drug use, alcohol use, and psychiatric diagnoses. The PI will train study staff regarding obtaining and handling potentially sensitive and private information about co-workers through staff discussions and written branch/section procedures. Information on drug and alcohol use will be in the participant's NIH medical record.

To ensure that sensitive information collected as part of this protocol remain as private as possible under the law, a Certificate of Confidentiality was obtained from the Department of Health and Human Services (DHHS).

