#### 4.5 Phenotyping Visit (Visit 1: Phenotyping)

The phenotyping visit will take place at the NIH Clinical Center up to 12 months before the exercise stress visit and is expected to last 5 days for HV and COVID-19 HV participants and 10 days for PI-ME/CFS participants. Phenotyping may occur on either an outpatient or an inpatient admission basis, depending on convenience. Information collected during the phenotyping visit will be used to determine PI-ME/CFS case status as well as to determine eligibility for the exercise stress visit. All procedures are for research purposes.

Consent will be obtained before any study procedures, including screening procedures, are done. Eligibility criteria will be reviewed during the consent process. An eligibility criteria checklist will be reviewed on Visit 1 completion and documented in the protocol's research records.

CNS IRB Protocol Template (2.5.15)

During the phenotyping visit, clinical information that is collected may impact participant eligibility. All participants in the PI-ME/CFS group will have documentation of being diagnosed with the illness in the community. In this way, PI-ME/CFS participants found not to meet inclusion/exclusion criteria during the phenotyping visit still represents what ME/CFS is in the community. For this reason, PI-ME/CFS participants that are found to have alterative or concomitant diagnoses that would otherwise exclude from study participation may still be invited to complete all of the phenotype visit procedures.

Participants in the HV and COVID-19 HV groups may be found to meet exclusion criteria during Visit 1. Such participants are also permitted to complete Visit 1 procedures, as long as they do not have substantial daily fatigue nor concerns for safety. Samples and data from these participants will be used in the primary analysis. HV and COVID-19 HV participants found to have substantial daily fatigue will have their study participation ended immediately and will not be used in primary analyses. Study participation for HV individuals meeting exclusion criteria will be complete at the end of Visit 1. Study participation for all COVID-19 HV individuals will be complete at the end of Visit 1.

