4.5.9 : Occupational Therapy Evaluation (only ME/CFS): Only ME/CFS participants may have an evaluation from occupational therapy. A licensed occupational therapist will perform an open-ended, focused interview intended to elicit perceptions of fatigue and its effect on function, in an unstructured format. The interviewer is free to ask additional questions to more fully understand the participant. Interviews to be digitally recorded and transcribed.

The Activity Card Sort – 2nd edition will also be administered. This is an instrument used for assessing participation in occupational performance of instrumental, socialcultural, and leisure activities. The tool uses a Q sort method in which respondents sort 89 cards depicting people engaged in various activities into 5 mutually exclusive categories, such as "never done," "continue to do," "recently added," "given up," and "do less." The Activity Card Sort yields a total score and four domain scores which can be used to determine a "retained activity level" score that is the percentage of activities in which a person is currently engaged in divided by those with whom he or she was involved in the past. The occupational therapy evaluation will take 60-90 minutes.

4.5.10 : Magnetic Resonance Imaging (MRI): A MRI of bilateral thighs and a structural brain MRI will be performed. Scanning will be performed either at Clinical Center Radiology or on a dedicated MRI scanner in the NMR Center. Scans may include clinical anatomic images, MPRAGE, DWI (for DTI) and T2w sequences. For the structural brain MRI, intravenous gadolinium contrast to determine cortical enhancement or meningeal inflammation will be given if there are no contraindications. MRI scans may include intravenous administration of an FDA-approved, macrocyclic, gadolinium-based MRI contrast agent (if applicable: including in healthy volunteers). Unless otherwise specified in the protocol, contrast agents will be used at FDA-approved doses. NIH Clinical Center Radiology and Imaging Sciences guidelines for gadolinium administration will be followed. Under certain circumstances, participants in this study may receive a linear chelate. Examples of situations in which this may occur include the following: (1) prior sensitivity to all macrocyclic agents; (2) participation in a longitudinal study in which a linear chelate was previously given, there is a clear advantage to maintaining the same

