gadolinium protocol, and T1 signal change in the basal ganglia or dentate nuclei was not observed; or (3) after consultation with, and approval by, a radiologist credentialed at the NIH Clinical Center. A list of the instances in which a linear chelate was administered, along with the justification for its administration, will be provided to the IRB at the time of continuing review. NIH Clinical Center Radiology and Imaging Sciences guidelines for gadolinium administration will be followed. Under certain circumstances, participants in this study may receive a linear chelate. Examples of situations in which this may occur include the following: (1) prior sensitivity to all macrocyclic agents; (2) participation in a longitudinal study in which a linear chelate was previously given, there is a clear advantage to maintaining the same gadolinium protocol, and T1 signal change in the basal ganglia or dentate nuclei was not observed; (3) after consultation with, and approval by, a radiologist credentialed at the NIH Clinical Center. A list of the instances in which a linear chelate was administration with, and approval by, a radiologist credentialed at the NIH Clinical Center. A list of the instances in which a linear chelate was administration with a linear chelate was provided to the IRB at the time of continuing review.

All NMR Center scans will be performed with dedicated radiofrequency coils that have received approval from the NIH Safety Committee. All women of childbearing potential will have a urine pregnancy test performed no more than 24 hours before each MRI scan. The blood and/or urine collections will be completed prior to MRI to screen for renal dysfunction or pregnancy that would be contraindicated for MRI (45-60 minutes).

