# 5.1.8 Transcranial Magnetic Stimulation (TMS)

TMS may be offered as an optional procedure for all participants. It may be performed a maximum on one time, either during Visit 1, prior to CPET during Visit 2, or as an additional outpatient visit. The optional TMS procedure will be performed only after a medication washout (if required) as detailed in Section 4.2.21. All women of childbearing potential will have a urine pregnancy test performed no more than 24 hours before each TMS session. The following paradigm will be utilized:

The subject will sit comfortably on a chair, with the right forearm placed in a rigid-frame dynamometer to measure the force generated by the muscles of the distal upper limb. The output of the dynamometer will be fed to a computer. We will determine MVC as the best of three wrist extensions. We will record the EMG by placing surface electrodes on the right forearm. A TMS-compatible EEG cap may be installed, in order to monitor the cortical activity during the TMS recordings and to allow the measurement of the cortico-muscular coupling during the muscular fatigue exercise.

Using a magnetic stimulator and figure-8 coil, we will determine the optimal position for evoking motor potentials (MEP) by holding the coil tangential to the scalp and slightly displacing it until the highest MEP amplitude will be recorded from the target muscle. The positions of subject's head and TMS coil will be tracked with a neuronavigation system, in order to maintain the stimulation position over the hotspot. We will then record the TMS Input-Output curve. For all subsequent TMS experiments, we will use the S50 stimulus level for the reference MEPs. Also, in this preparatory phase, we will record the maximum M-wave by applying electrical stimulation with surface electrodes on the nerve innervating the target muscle. All MEP amplitudes will be normalized to each subject's Mmax amplitude.

The TMS evaluation will begin with a block of 100 single pulses delivered every 5 seconds in order to allow the subsequent analysis of the EEG responses. This battery will be followed by a short set of double-pulses for measuring short intracortical inhibition (SICI) and intracortical facilitation (ICF).

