## 9.10 Risks of MRI

Participants may be at risk for injury from the MRI magnet if they have some kinds of metal in their body. It may be unsafe for participants to have an MRI scan if they have a pacemaker or other implanted electrical device, brain stimulator; some types of dental implants, aneurysm clips, and metallic prostheses (including metal pins and rods, heart valves, and cochlear implants); permanent eyeliner; implanted delivery pump; or shrapnel fragments. Welders and metal workers may have small metal fragments in the eye. Participants will be screened for such metal before having any scan. If they have any, you will not receive an MRI scan. If they have a question about metal in their body, they should inform the study investigators. Participants will be asked to complete an MRI screening form before each MRI scan they have.

All magnetic objects must be removed before entering the MRI scan room. This includes items like watches, coins, jewelry, and credit cards.

It is not known if MRI is completely safe for a developing fetus. Therefore, all women who are able to get pregnant will have a pregnancy test done no more than 24 hours before each MRI scan. The scan will not be done if the pregnancy test is positive.

People with fear of confined spaces may become anxious during an MRI. Those with back problems may have back pain or discomfort from lying in the scanner. The noise from the scanner is loud enough to damage hearing, especially in people who already have hearing loss. Everyone having a research MRI scan will be fitted with hearing protection. If the hearing protection comes loose during the scan, participants should let us know right away.

Symptoms from the contrast infusion are usually mild and may include feeling hot, burning, or

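### Section 13.9 lets an admission pregnancy test stand for the whole inpatient stay, which conflicts with the 24-hour limit that sections 4.5.10, 9.10 and 5.1.8 set before MRI and TMS; the main gap is an inpatient Visit 1 MRI at Clinical Center Radiology

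*Combined protocol and SAP*

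**What the plan says.** Section 13.9 (safeguards) requires a urine pregnancy test at admission for Visit 1 and Visit 2, and then states: "This pregnancy test will be considered valid for the entire period of the inpatient admission". It goes on to list further tests: "additional pregnancy testing will be performed 24 hours prior to MRI scans performed in the NIH NMR center", and also "prior to the use of ionizing radiation, such as DEXA, and fluoroscopy-guided LP". MRI at Clinical Center Radiology and TMS are not on that list.

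The procedure and risk sections give a time limit:

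- Section 4.5.10 (Visit 1 MRI): "All women of childbearing potential will have a urine pregnancy test performed no more than 24 hours before each MRI scan".
- Section 9.10 (risks of MRI): women able to become pregnant "will have a pregnancy test done no more than 24 hours before each MRI scan". A positive result stops the scan.
- Section 5.1.8 (TMS): "All women of childbearing potential will have a urine pregnancy test performed no more than 24 hours before each TMS session".

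Section 4.5.10 also leaves the location of the Visit 1 MRI open: "Scanning will be performed either at Clinical Center Radiology or on a dedicated MRI scanner in the NMR Center". Gadolinium is given for the structural brain scan unless contraindicated.

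**The concern.** A test that counts for a whole admission and a test that must be less than a day old are different rules. For an inpatient scanned at Clinical Center Radiology several days into Visit 1, 13.9 accepts the admission test, while 4.5.10 and 9.10 do not. Staff who work from the safeguards section would depart from the procedure and risk sections.

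The protocol itself treats the test as a safety control. Section 9.10 says the safety of MRI for a fetus is not established, section 13.3 calls pregnancy a contraindication for MRI, and section 3.3.1 excludes pregnant women. The scan is a research procedure without direct benefit to the participant. Under 13.9, the age of the test behind the same scan would depend on which scanner was used. No endpoint or analysis is affected.

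**Working it through.** There is no sample size, power or error rate to recompute. The check sets the testing rules side by side for each procedure, then works out how old an admission test could be.

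**Rules by procedure**

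| Procedure | Section 13.9 | Procedure or risk section | In conflict? |
|---|---|---|---|
| Visit 1 MRI, Clinical Center Radiology, inpatient | Admission test stands; no retest named | 24 hours (4.5.10, 9.10) | Yes |
| Visit 1 MRI, NMR Center | Retest at 24 hours | 24 hours (4.5.10, 9.10) | No |
| fMRI at Visit 2 (and optional fMRI at Visit 1, same procedure by 5.1.7) | Retest at 24 hours, since all of it is at the NMR Center (4.6.17) | 24 hours (4.6.17) | No |
| TMS during an inpatient stay | Not on the retest list; the whole-stay sentence would cover it | 24 hours (5.1.8) | Yes, through the whole-stay sentence only |
| DEXA | Retest, interval not given | 24 hours (4.6.9) | No; 4.6.9 supplies the interval |
| Any outpatient visit | Whole-stay sentence does not apply | As above | No |

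Section 4.6 adds that testing always precedes MRI, fMRI and TMS at Visit 2. It gives no window, so an admission test would satisfy it.

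**Age of the admission test at a Visit 1 MRI or TMS session**

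Upper bound on the age = length of stay up to the procedure, which is at most the full stay. Ratio = hours of stay / 24.

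- Précis, stay of 2 to 5 days: 2 × 24 = 48 h and 5 × 24 = 120 h. Ratios: 48/24 = 2 and 120/24 = 5.
- Section 4.5, where the visit "is expected to last 5 days for HV and COVID-19 HV participants and 10 days for PI-ME/CFS participants": 5 × 24 = 120 h and 10 × 24 = 240 h. Ratios: 5 and 10.

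The two descriptions of the length of Visit 1 themselves disagree, so both ranges are shown. Section 4.5 also allows Visit 1 to be done as an outpatient, and then 13.9 does not extend an earlier test.

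**Age of the admission test at a Visit 2 TMS session**

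Section 5.1.8 requires Visit 2 TMS to come before the exercise test, and participants stay for observation afterwards. Upper bound = stay minus observation.

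- 72 hours of observation (section 4.6), stay of 5 to 10 days: 5 − 3 = 2 days and 10 − 3 = 7 days.
- Up to 96 hours (Précis): 5 − 4 = 1 day and 10 − 4 = 6 days.

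This assumes discharge once observation ends. It is shorter than the full stay on either figure.

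**Number affected**

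The documents do not give it. The 150 main-study places (3 groups × 50) are an accrual ceiling, and the completion target is 20 per group. Neither figure separates women of childbearing potential, inpatients, or scans at Clinical Center Radiology.

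**The case against.** The strongest reply is that the rules can all be met together. Section 13.9 does not contain the word *only*, forbids nothing, and introduces its further tests as additions. A site that tests at admission and again within 24 hours of every scan and TMS session complies with every section. This stands as far as it goes: the documents do plan 24-hour tests, and following 4.5.10, 5.1.8 and 9.10 closes the gap. It does not remove the conflict, because 13.9 expressly declares an older test valid and no section is given precedence.

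A second reply is that the 24-hour sentence in 4.5.10 follows one about NMR Center coils and may be meant for that center alone. It is worded for each scan, however, and 9.10 carries no limit by location.

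Third, for TMS, silence in a list is not a contradiction. That is fair: 5.1.8 is explicit, and TMS is optional and done at most once. The conflict there comes only from the whole-stay sentence, so TMS is a secondary case.

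A reader might also infer that every scan and TMS session at both visits could rest on a test 5 to 10 days old, or that up to 150 people are exposed. The documents do not support either. Visit 2 fMRI is retested under 13.9 itself, Visit 2 TMS falls before the exercise test, Visit 1 may be short or outpatient, and 150 is a ceiling on enrollment.

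**Conclusion.** The inconsistency is real and narrow. For an inpatient Visit 1 MRI at Clinical Center Radiology, 13.9 accepts a test as old as the stay to that point: up to 2-5 days by the Précis, or up to 5 or 10 days by section 4.5, against 24 hours in 4.5.10 and 9.10. Inpatient TMS is a lesser case with the same source.

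The conclusion assumes that staff could reasonably treat 13.9 as a complete rule, that the MRI or TMS comes late in the stay, and that no document outside those supplied sets the order of precedence. It does not show that an old test has been or will be used. A mismatch with the consent forms might also be suspected, but those forms are not among the documents, so none can be shown. The point deserves correction because it concerns a stated safety control and is cheap to resolve.

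**What to change.** Amend 13.9 so that its whole-stay sentence and its wording limited to the NMR Center agree with 4.5.10, 5.1.8 and 9.10 on how old a test may be before MRI at either location and before TMS. Alternatively, state which section governs. Whichever rule is kept, make the risk text in 9.10 match it. This review takes no view on which interval is right, and the point does not call for a new uniform interval across all procedures.

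The cost is amendment wording in one section, with matching edits elsewhere if the other rule is kept. Depending on the choice, some inpatients would have a repeat urine test, which the protocol already uses.

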# 14 Anticipated Benefit: Indirect

This study does not offer direct benefit to participants but is likely to yield generalizable knowledge about ME/CFS.

#### **15** Consent Documents and Process

The following section describes the informed consent process for participating in scientific protocol at NIH. The informed consent process for focus group participants is described fully in Section 4.3.

#### 15.1 Consent procedures

All participants will receive a verbal explanation in terms suited to their comprehension of the purposes, procedures and potential risks of the study and of their rights as research participants. Participants will have the opportunity to carefully review the written consent form and ask questions regarding this study prior to signing. Participants who have completed participation (prior to Amendment 11) will be offered the opportunity to complete missing research procedures and undertake optional procedures made available in prior Amendments. These individuals will complete a written re-consenting process with the most recent version of the informed consent form. Persons who have completed participation (prior to approval of Amendment I) will also be offered the option of undergoing whole genome sequencing. These individuals will be contacted by email or telephone to determine if they are interested. Interested participants will be mailed a copy of the whole genome sequencing informed consent form. The individual will be instructed to read the consent form and be ready at the agreed upon date and time to review the consent document with an investigator authorized to obtain consent.

The consenting investigator will document the date and time oral consent was obtained on a consent procedure note. The participant will sign and date the consent form in the presence of a witness. The witness will also sign and date the consent form. The subject will be instructed to mail the consent form back to the site, where the investigator will sign and date the form. The investigator will then send a copy of the form with all signatures to the subject. The original consent document will be placed in the research chart.

#### 15.2 Consent documents

The consent form contains all required elements. One consent form will be used for ME/CFS and HV participants in the main study (ME/CFS, HV Consent Form). A separate consent form will be used for COVID-19 HV participants in the main study (COVID-19 HV Consent Form). Two separate consent forms will be used for participants in Focus Group A and for Focus Group B. A separate consent form will be used for substudy Consent Form). A separate consent for will be used for participants in the technical development sub-study (Technical Development Substudy Consent Form). A separate consent for will be used for obtaining consent for whole genome sequencing (Whole Genome Sequencing Consent Form).

#### 16 Data and Safety Monitoring

#### *16.1* Data and safety monitor

Data and safety will be monitored by the Principal investigator in conjunction with an independent medical monitor. The independent medical monitor is [name].

#### 16.2 Data and safety monitoring plan

Study investigators will evaluate the safety of study subjects throughout the conduct of the study and respond to adverse events (AEs) in a timely manner. The PI in collaboration with associate investigators will review any cases associated with serious adverse outcomes and advise on whether or not any changes in the research plan are warranted. Data and safety monitoring will occur annually,

